### 5.3.2 Drug-drug Interactions

Drug-drug interactions of MGD013 have not been evaluated in clinical studies. Bispecific antibodies to MGD013, for example, are not substrates for cytochrome P450s or drug transporters and are not likely to be cytokine modulators. No PK DDI is expected between MGD013 and small molecule drugs.

In five drug-drug interaction (DDI) studies in human, no drug-drug interactions were detected in humans when brivanib alaninate was co-administered with CYP3A4 substrates, CYP2C8 substrates, CYP3A4 inhibitors, and P-gp substrates without dose adjustment. Concomitant Rifampin should be avoided for it can significantly lower the exposure to Brivanib.

# 5.3.3 Best supportive care

All subjects participating in this clinical study are allowed to receive best supportive care (BSC). The BSC will be defined according to the institutional standards of the participating clinical centers. In general, BSC should be understood as a multi-professional focus on the overall physical, psychosocial, spiritual and cultural needs of the subjects at all stages of disease. This concept is applicable to the subjects of all ages and is independent of the intent of any anticancer therapy (EORTC Pain and Symptom Control Work Team). Based on the physical health status of HCC subjects participating in this study, BSC may include, but is not limited to: (1) analgesics, including non-steroidal anti-inflammatory drugs, opioids, etc.; (2) antiemetics; (3) vitamins and nutritional support; (4) hepatoprotective and choleretic therapy; (5) bisphosphonates for bone metastases, etc. Loco-regional radiation therapy is allowed to reduce symptoms, such as the pain caused by non-target lesions, as long as the total dose of treatment is within the palliative range specified by institutional standards. Palliative radiotherapy to the target lesion is not allowed if the subject is taking investigational drug. If jaundice is caused by obstruction of the biliary tree, percutaneous intrahepatic biliary drainage may be adopted.

### **5.4 Treatment Compliance**

Brivanib alaninate is dispensed to subjects by trained medical personnel. It will be dispensed at the study center pharmacy and will be self-administered by subjects. Subjects must record the investigational drug administration information in the study diary provided by the Sponsor. At each visit, subjects must bring back the diary as well as all unused investigational drug and empty packing boxes or bottles. Compliance will be assessed by the investigator and/or study staff through the count of tablets and information provided by the subjects or caregivers. At each visit, the administration information of investigational drug (including planned administration dose, actual administration dose, dose change, administration interruption, etc.) must be recorded in the source documents and in the eCRF.

Each dose of MGD013 will be administered at the study site and will be prepared and infused by trained medical staffs. The administration information of MGD013 (administration dose, infusion time, whether there is infusion reaction, etc.) should also be recorded in the source documents and in the eCRF.

It is investigator's and site staff's responsibility to evaluate and analyze potential noncompliance (such as AEs or missing dose) at the beginning and during the study with the sponsor's monitor, and to consider and implement strategies for improving medication compliance in advance.

### 5.5 Investigational Drug Management

### 5.5.1 Packaging and Storage

Brivanib alaninate tablets are supplied in tightly closed high-density polyethylene (HDPE) bottles with desiccant canisters. The bottles are heat-induction sealed with child-resistant

closures. MGD013 is supplied in 20 mL (single-dose) Type I USP and EP borosilicate clear glass vial, which is capped with a 20 mm FluroTec®-coated 4023/50 gray butyl rubber stopper. It is sealed with a 20 mm aluminum-plastic lid. Brivanib alaninate shall be stored at 10 - 30 °C in a tightly closed container. MGD013 should be stored at 2°C - 8°C. All investigational drugs for treatment must be stored in accordance with sponsor and manufacturer's instructions. They will be placed in access control places with locks that meet storage conditions and comprehensive safety precautions.

All investigational drugs will be numbered according to the requirements of Good Manufacturing Practice (GMP). The label text should include drug name, strength, package, sponsor name, batch no., and expire date, protocol no., and administration and so on.

## 5.5.2 Responsibilities for Reception, Storage, and Management of Investigational Drugs

It is the responsibility of the investigator to manage the investigational products and equipment on its study site that are provided by the sponsor. The investigational products and supplies must be recorded accurately in accordance with the protocol and national laws and regulations, supplied as required by the study at any time and maintained, stored, dispensed, used and disposed according to the regulations. A specialized person should be designated by the investigator to receive, store, dispense and return all investigational products during the study, and to record the dispensing accurately. Drug dispensing management form should include subjects' identification number, random number, number of the dispensed, number of drug bottles and number of the returned. Drugs returned from subjects to study sites must be marked with "returned" to distinguish them from those that are not dispensed.

All dispensing and management records should be accessible to the Sponsor for review. Study monitors will verify according to drug dispensing management form and stored drugs. Designated drug managers will dispense the investigational drugs according to the study protocol and drug management manual and cooperate with monitors' audit.

## 6. Visit Schedule and Assessments

### 6.1 Study visits and assessments

## **6.1.1 Screening Period** (Day-28 to Day0)

The following examinations or tests are required to be completed during the screening period:

- Signing ICF;
- Recording demographics: date of birth, gender, race, tobacco use, alcohol intake history, etc.;
- Medical history and physical examination;
  - Medical and surgical history
  - Past and present medical history of HCC, including the date of first diagnosis, pathological type of tumor, BCLC stage of initial diagnosis, history of surgical or loco-regional treatment, systematic treatment history, cause of disease, BCLC stage at enrollment, Child-Pugh liver function classification, etc.
  - Physical examination and vital signs (within 7 days before administration), including height, weight and systemic examination; ECOG performance status score;
- Hematologic test (complete blood cell count, CBC differential count): within 7 days before administration;
- Serum biochemistry (within 7 days before administration): including liver function (total bilirubin, alanine aminotransferase, aspartate aminotransferase, γ-GT, alkaline phosphatase, lactate dehydrogenase, serum total protein and albumin, etc.), renal function (urea nitrogen or urea, creatinine), electrolytes (K, Na, Cl, Ca, serum phosphorus, serum magnesium), fasting blood glucose, amylase, lipase;
- Thyroid function (TSH, free T3, free T4), within 7 days before administration;
- Coagulation (TT, PT, APTT and INR), within 7 days before administration;
- AFP test within 7 days before administration;
- Urinalysis (urine protein, urine occult blood, urine red blood cell, urine glucose, white blood cell, urine specific gravity, PH value), within 7 days before medication;
- 12-lead ECG, within 7 days before administration;
- Echocardiography (performed during the screening period, and whether examinations are required at subsequent visits is determined according to clinical needs);
- Blood or urine HGG for female subjects with childbearing potential (except females who have underwent surgical sterilization or those have been menopausal for more than one year) to exclude pregnancy (within 7 days before administration);
- Hepatitis B serologic test, and HBV-DNA (only when HbsAg is positive);
- Anti-HCV antibody, HCV-RNA (only when HCV antibody is positive);
- HIV serology;
- RECIST 1.1 assessment (During the screening period, contrast-enhanced CT on the chest as well as contrast-enhanced CT/MRI on the abdomen and pelvis are

required; contrast-enhanced CT/MRI on the abdomen and other clinically indicated sites are performed for subsequent assessments);

- Brain MRI (To rule out brain metastasis as indicated clinically);
- Assessment of previous and concomitant medications (it is required to collect the medication history within 30 days prior to signing the ICF);
- Evaluation of adverse events;
- Eligibility assessment based on inclusion and exclusion criteria (review on results of diagnostic examination, and assessment of inclusion and exclusion criteria);

### 6.1.2 Cycle 1

## 6.1.2.1 Cycle 1, Day 1

- Physical examination (to assess the changes since screening period) and body weight
- Vital signs (respiratory rate, Blood Pressure (BP), heart rate, body temperature): on Cycle 1 Day 1, vital signs are examined at the following time points: prior to infusion of MGD013 (within 30 minutes prior to infusion), at 15, 30 minutes (± 5 minutes) after infusion, at the end of infusion (± 10 minutes), at 1, 3 hours (± 10 minutes) after the completion of infusion.
- ECOG body performance status score
- 12-lead ECG
- Evaluation of adverse events
- Evaluation of concomitant medication
- Dispense investigational drug and medication diary
- Completion of intravenous infusion of MGD013 at study sites
- Administration of the first dose of brivanib alaninate (combination therapy group)

### 6.1.2.2 Cycle 1, Day 8

- Vital signs (respiration, blood pressure, heart rate, body temperature)
- 12-lead ECG
- Hematology
- Serum biochemistry
- Coagulation
- Evaluation of adverse events
- Evaluation of concomitant medication

### 6.1.3 Cycle 2

### 6.1.3.1 Cycle 2, Day 1

- Physical examination (to assess the changes since screening period) and body weight
- Vital signs (respiration, BP, heart rate, temperature): prior to infusion of MGD013 (within 30 minutes prior to infusion), at the end of infusion ( $\pm$  10 minutes), at 1

hour ( $\pm$  10 minutes) after the completion of infusion.

- ECOG body performance status score
- 12-lead ECG
- Hematology
- Serum biochemistry
- Coagulation
- Urinalysis
- Evaluation of adverse events
- Evaluation of concomitant medication
- Return Investigational Drug and Review Medication Diary
- Completion of intravenous infusion of MGD013 at study sites
- Dispensing of the investigational drugs and medication diary (combination therapy group)

## 6.1.3.2 Cycle 2, Day 8

- Vital signs (respiration, blood pressure, heart rate and body temperature)
- 12-lead ECG
- Hematology
- Serum biochemistry
- Coagulation
- Evaluation of adverse events
- Evaluation of concomitant medication

## 6.1.4 Day 1 of subsequent cycles

- Physical examination (changes since the previous assessment) and body weight
- Vital signs (respiratory rate, BP, heart rate, body temperature): prior to infusion of MGD013 (within 30 minutes prior to infusion), at the end of infusion (± 10 minutes), at 1 hour (± 10 minutes) after the completion of infusion.
- ECOG body performance status score
- 12-Lead ECG
- Hematology
- Urinalysis
- Coagulation test
- Serum biochemistry
- Serum AFP: once every 8 weeks (±7 days) until disease progression, test corresponding to radiographic assessment
- Assessment according to RECIST 1.1 and irRECIST: once every 8 weeks (± 7 days) until disease progression, tumor evaluation of pelvic and abdominal cavity and other sites as clinically indicated

- Thyroid function: once every two cycles ( $\pm 3$  days)
- HBV-DNA (HBsAg positive subjects), once every 8 weeks ( $\pm$  7 days)
- HCV-RNA (HCV antibody positive subjects), once every 8 weeks (± 7 days)
- Evaluation of adverse events
- Evaluation of concomitant medication
- Dispense investigational drug and recover medication diary (combination therapy group)
- Completion of intravenous infusion of MGD013 at study sites (for at most 48 cycles)

# 6.2 End of Study Treatment (completion of visits within 7 days after last dose of investigational drugs/withdrawal)

- Physical examination and body weight
- Vital signs (respiration, blood pressure, heart rate, body temperature)
- ECOG body performance status score
- 12-Lead ECG
- Hematology
- Urinalysis
- Coagulation test
- Blood or urine pregnancy test (for female with childbearing potential)
- Serum biochemistry
- Serum AFP
- Thyroid function
- Evaluation of AEs (un-recovered or new AEs need to be assessed and recorded after this visit until 30 days after the last dose of investigational drug; in case of serious AEs or AESIs, the subject will be followed continuously until recovery or stabilization of the adverse event.)
- Evaluation of concomitant medication
- Return the investigational drugs and medication dairy (combination therapy group)

Note: If the corresponding laboratory tests or examinations are performed within 7 days, it is not necessary to repeat them.

# 6.3 Safety Follow-up (30 days $\pm$ 7 days after end of study treatment)

- Physical examination
- Hematology
- Blood chemistry
- Evaluation of AEs (investigational drug-related SAEs after this visit should be evaluated and recorded)
- Evaluation of concomitant medication

# 6.4 Post-Treatment Assessments (Subjects in phase II are not required to have visits in the study site)

- Subjects will receive survival follow-up and subsequent treatment follow-up to collect
  - the information (including commencement date of subsequent first anti-tumor treatment) of first anti-tumor treatment (including chemotherapy) after the end of study treatment every 60 days (± 7 days)
  - Subjects will receive survival follow-up after discontinuation of study treatment every 60 days (± 7 days) to collect the information of new malignant tumors
- Monitoring of SAEs and irAEs: study treatment-related SAEs or irAEs ≥ grade 3 occurring within 30 days after the last dose should be recorded and evaluated.
- Tumor imaging assessments and serum AFP: If the subject is withdrawn from the treatment for reasons other than radiographic progression, the subject will still need to undergo imaging scans and AFP testing every 8 weeks (± 1 week) after discontinuation of study treatment until tumor progression is confirmed or subsequent antineoplastic therapy is initiated

# 7. Study Endpoints

### 7.1 Safety Assessments

## 7.1.1 Laboratory Tests

The laboratory tests will be performed at the study site in accordance with the schedule of study visits in Table 1. Table 3 listed required laboratory tests of this study. Specific items included in hemotology, biochemistry, coagulation tests and urinalysis could be adjusted based on local practice of each site.

Females subjects (except females who have underwent surgical sterilization and those have been menopausal for more than one year) of childbearing potential should undergo pregnancy test. The frequencies of all laboratory tests will be determined according to the schedule of study visits, but unscheduled tests may be added according to the clinical judgment by the investigator. All test results should be filed in the original case report and recorded in the eCRF.

Table 3. Laboratory tests

Haematological examination (CBC)	Clinical Chemistry (Serum) and Coagulation	Urinalysis
Red cell count	Blood urea nitrogen or urea, creatinine	Specific Gravity
Hemoglobin	Albumin, total protein	White blood cell
Packed cell volume	LDH, blood glucose	Occult blood, red blood cell
Classification of leukocytes and absolute count (neutrophils, basophils, eosinophils, lymphocytes, monocytes)	Alkaline phosphatase (ALP), GGT, ALT, AST, total bilirubin	Glucose
Platelet count	Sodium, potassium, calcium, magnesium, chloride	Protein, PH
	Amylase, lipase	
	Activated partial thromboplastin time APTT, international standardization ratio INR	

### 7.1.2 Electrocardiogram Assessment

12-lead ECG examination will be performed according to Table 1 Schedule or at the time when any cardiac-related adverse event occurs during the study. Examination should be performed after the subject has rested in the supine position for at least 10 minutes prior to the specified time point. Each examination should be performed in the same position and all ECGs should be recorded. At each time point, the record of 2 ECGs with 2 minutes apart, should be obtained. A standardized electrocardiograph machine should be used, and the same device should be used throughout the study if possible.

All ECG assessment items will include parameters such as heart rate, QRS complex, QT interval, QTc, and RR interval. ECG results will be assessed by the investigator or specialist and will be recorded in the eCRF. If a clinically significant abnormality is found at baseline (screening), it should be recorded in the subject's medical history; if a clinically significant abnormality is reported during treatment, it will be reported as an AE.

### 7.1.3 Physical examination

A standard physical examination (including appearance, skin, eyes, ears/nose/throat, head and neck, heart, chest and lungs, abdomen, extremities, lymph nodes, musculoskeletal, nervous system, and other body systems, as applicable) will be performed according to Table 1 schedule of study visits. Height is measured at the screening visit only.

## 7.1.4 Vital signs

Vital signs (respiratory rate, heart rate, blood pressure, and body temperature) will be measured according to Table 1 schedule of study visits. Vital sign should be measured in a sitting position after at least 10-minute's rest. Vital signs are only examined once at the visit in the screening period and that at the end of study; on Cycle 1 Day 1, vital signs are examined at the following time points: prior to infusion of MGD013 (within 30 minutes prior to infusion), at 15, 30 minutes ( $\pm$  5 minutes) after infusion, at the end of infusion ( $\pm$  10 minutes), at 1, 3 hours ( $\pm$  10 minutes) after the completion of infusion. For subsequent visits, vital signs are examined at the following time points: prior to infusion of MGD013 (within 30 minutes prior to infusion), at the end of infusion ( $\pm$  10 minutes), at 1 hour ( $\pm$  10 minutes) after the completion of infusion. Additional vital signs examination may be performed at any other time points as clinically indicated.

## 7.1.5 Eastern Cooperative Oncology Group (ECOG) Performance Status Score

ECOG performance status scoring will be evaluated according to Table 1 schedule of study visits. Refer to Table 4 for scoring.

Table 4. ECOG score

Description of physical status	
Completely normal, being able to perform work before illness without restriction	0
Not able to carry out heavy physical work, but be able to walk around and carry out light physical work such as light housework or office work	1
Can move around, capable of self-care, but unable to carry out any work-related activities, confined to bed for less than 50% of the day	2
Self-care can only be achieved to a limited extent, with more than 50% of the daytime spent in bed rest or chair sitting	3
Complete loss of activity of daily living, unable to achieve selfcare, confined to bed or wheelchair	4

### 7.1.6 Echocardiography

Echocardiogram for LVEF is to be done at baseline, and then performed as clinically indicated (e.g. cardiac symptoms, or abnormal ECG findings with clinical significance).

## 7.2 Efficacy assessments

Contrast-enhanced CT or MRI of abdomen, pelvic and contrast-enhanced CT of lungs are required at baseline. During the follow-up visit, the same method of radiologic assessment on abdomen, pelvic cavity and other clinically indicated sites should be used. All baseline tumor imaging assessments must be performed within 28 days prior to the start of study medication. If subjects receive scanning before signing an informed consent form, as long as the scanning imaging is within the time limit specified by the protocol, the test method meets the requirements for image collection, and the data are obtained, it can be used for study analysis.

Radiologic examination should be conducted on abdomen, pelvic cavity and other clinically indicated sites every 8 weeks (±7 days) dated from the first day of the first cycle until disease progression. All imaging of Phase II study must be evaluated by independent central review.

Tumor assessment should be carried out in strict accordance with the study plan. If imaging assessment occurs beyond the planned visits and there is no disease progression, subsequent tumor assessments should still be carried out **according to the original plan**.

The investigator will also evaluate imaging response by RECIST 1.1 and irRECIST criteria, and classify the objective tumor response by target lesion assessment into: CR, PR, SD, PD and NE. For the subjects with initial response as PR or CR, the response should be confirmed at an interval of at least 4 weeks. subjects should be administered until PD confirmed according to irRECIST.

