#### **Secondary Efficacy Endpoints:**

Phase I: irRECIST-based ORR.

Phase II: secondary efficacy endpoints of phase II study include:

BICR-assessed ORR according to irRECIST; Investigator-assessed ORRs according to RECIST 1.1 and irRECIST respectively;

Disease control rate (DCR): defined as the proportion of enrolled subjects with best response of CR, PR or SD assessed using RECIST 1.1 and irRECIST criteria respectively.

Time to tumor progression (TTP): defined as the time from the first administration to the time of radiographic disease progression under RECIST 1.1 and irRECIST criteria. Subjects without documented

radiographic progression due to loss to follow-up or changing treatment regimen during follow-up will be censored on the last radiographic follow-up date on which no disease progression is confirmed.

Duration of response (DoR): defined as the time from radiographic response to disease progression or death in subjects whose best response is CR or PR. DoR is assessed with RECIST 1.1 and irRECIST criteria respectively

Progression-free survival (PFS): defined as the time from the first dose to the date of tumor progression or death due to any cause. Disease progression is assessed using RECIST 1.1 and irRECIST criteria respectively. Subjects without documented radiographic progression or death during follow-up will be censored on the last follow-up date on which no disease progression is confirmed. For subjects without progression till the date of analysis, they will be censored on the last tumor assessment date.

Overall survival (OS): defined as the time from first administration to death caused by any reason. Subjects who are alive during the follow-up or are lost to follow-up without documented death will be censored on their last known alive date. For subjects alive till the date of analysis, they will be censored on their last known alive date.

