### Schematic diagram of the study:

Each cohort will enroll approximately 30 evaluable advanced HCC subjects who progressed after immune checkpoint inhibitor treatment, and approximately 40 evaluable advanced HCC subjects who have not previously received immune checkpoint inhibitor treatment. The SWOG two-stage design will be employed. In the first stage, 20 advanced HCC subjects who have not previously received immune checkpoint inhibitor treatment will be enrolled. If response is observed in 3 or more subjects (according to RECIST 1.1), the enrollment of second stage will be open and an additional of 20 evaluable subjects will be enrolled. The enrollment of advanced HCC subjects who have previously received immune checkpoint inhibitor treatment will be similar, there are 2 stages for the group and the response (according to RECIST 1.1) of 1 and more out of 15 evaluable subjects at the first stage will support the decision to proceed to the second stage of subject accrual until there are 30 evaluable subjects in this group. If the response in any treatment group is found less than the above standard in the first period, the enrollment of second stage will be terminated.

In Phase II study, 2 weeks (14 days) will be defined as a cycle, and subjects will continue to receive study treatment until disease progression (according to irRECIST), death or the occurrence of intolerable toxicity (whichever comes first). MGD013 will be administered for

at most 48 cycles. If subjects do not have disease progression after discontinuing MGD013, subjects of the combination therapy group may continue brivanib alaninate.

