## 4.3 Discontinuation of Subjects from Treatment

### 4.3.1 End of Treatment

Subjects may discontinue treatment at any time during the study. End of Treatment Visit (EOT) should be performed within 7 days of decision date to discontinue treatment.

Study drug shall be permanently discontinued in any of the following cases:

- Adverse Event
  - Occurrence of any CTCAE (V5.0) grade 3 or 4 treatment-related adverse event, which fails to recover to CTCAE Grade 1 or below within 4 weeks (28 days) (unless the investigator believes that the subject may continue to benefit from treatment and the continuation requires the permission from sponsor's medical monitor);
  - CTCAE Grade 3 or 4 treatment-related adverse event recurs in combination treatment group despite dose reduction of brivanib alaninate;
  - Myocardial ischemia and/or infarction;
  - Evidence for abnormal cardiac valve function ≥ CTCAE Grade 2;
  - LVEF decrease by > 10% from baseline-ECHO and LVEF < 45%;
  - QTc > 500 milliseconds on 3 consecutive ECGs performed during the same visit and in the absence of possible causes other than study therapy;

- Torsade de pointes or sustained ventricular tachycardia;
- Hemorrhage ≥ CTCAE Grade 3;
- Gastrointestinal perforation;
- Arterial thromboembolic event;
- Venous thromboembolic events of CTCAE Grade 3 or 4;
- Hypertensive crisis;
- Immune-related adverse events of grade 4.
- Disease progression according to irRECIST criteria
- Risk to the subject as judged by the investigator and/or sponsor
- Critical violation to the protocol as judged by the investigator and/or sponsor
- Subject's decision
- Pregnancy
- Death
- Completion of protocol-defined therapy (MGD013 monotherapy)

If the reason for treatment discontinuation is not disease progression, death, withdrawal of informed consent or loss to follow-up, radiologic tumor assessments will still be performed at protocol-specified intervals until disease progression by irRECIST or the starting of subsequent antitumor therapy (Phase II).

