#### 2.4.1 Time Point Response

It is assumed that at each protocol specified time point, a response assessment occurs. For patients experiencing irCR or irPR, a confirmatory scan obtained no less than 4 weeks after the original scan is required to confirm the objective response. For patients experiencing

irPD, but who demonstrate acceptable tolerability of treatment as evaluated by the Investigator, a

confirmatory scan obtained no less than 4 weeks after the original scan is required for the confirmation of irPD.

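### Sections 3.1.4 and 4.3.1 end study drug at irRECIST progression, section 7.2 only at confirmed irRECIST progression, and after a stop at first irPD no scan is clearly scheduled to confirm it

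*Combined protocol and SAP*

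**What the plan says.** Treatment stop:

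- Section 3.1.4 (Phase II): "subjects will continue to receive study treatment until disease progression (according to irRECIST), death or the occurrence of intolerable toxicity". The same section later says that investigators should preferably use irRECIST to judge progression that requires stopping.
- Section 4.3.1: "Study drug shall be permanently discontinued in any of the following cases". The list that follows includes "Disease progression according to irRECIST criteria", with no reference to confirmation.
- Section 7.2: "subjects should be administered until PD confirmed according to irRECIST".
- Appendix B 2.4.1: for patients with irPD who tolerate treatment acceptably, a "confirmatory scan obtained no less than 4 weeks after the original scan is required for the confirmation of irPD".

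Imaging:

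- Section 7.2 schedules scans every 8 weeks (±7 days) until disease progression.
- Section 4.3.1, on scans carried out after a stop: "If the reason for treatment discontinuation is not disease progression, death, withdrawal of informed consent or loss to follow-up, radiologic tumor assessments will still be". Section 6.4 likewise limits post-treatment imaging to stops other than radiographic progression.
- Table 1 footnote 6 continues imaging unless the stop was for progression that is unequivocal. It asks for a confirming scan after a first CR or PR and is silent on irPD.

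Endpoints:

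- The synopsis defines PFS and TTP under both RECIST 1.1 and irRECIST. A PFS subject with neither documented radiographic progression nor death "will be censored on the last follow-up date on which no disease progression is confirmed".
- Appendix B 2.4 counts best overall response only up to the end of treatment.
- Appendix B 2.5.2 ends duration of response at the first date on which progression is documented.

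**The concern.** The stopping rule is written in two forms, and both stand in operative text. A site working from 4.3.1 stops drug at the first scan meeting irPD. A site working from 7.2 continues until a second scan confirms it. The imaging rules do not repair the difference: once a subject has been stopped for progression, the confirming scan that Appendix B asks for is not clearly on the schedule.

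Three things are at stake. Exposure, and with it the period at risk for adverse events, can differ between subjects with the same scans. A first irPD that a later scan would have overturned can be detected at one site and not at another. And the irRECIST secondary endpoints are built on an event that the definitions do not fix as first or confirmed irPD.

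**Working it through.** The plan gives no figure on this point to reproduce, so the check is a comparison of passages, followed by arithmetic for exposure.

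**1. Is confirmation part of irPD itself?** Appendix B 2.3.1 and the notes to its response table define irPD at one time point, as an increase of at least 20% in the sum of diameters over the smallest sum on study. Confirmation appears separately, in 2.4.1, and only for subjects who tolerate treatment. A reader of 3.1.4 or 4.3.1 who looks up irRECIST progression can therefore arrive at either the first or the confirmed irPD.

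**2. One subject, two sections.** Suppose a subject who tolerates treatment first meets irPD at a scheduled scan.

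| | Following 3.1.4 and 4.3.1 as worded | Following 7.2 and Appendix B 2.4.1 |
|---|---|---|
| Study drug | stops at first irPD | continues to the confirming scan |
| Next scan | none under 4.3.1 or 6.4, because the stop was for progression | at least 4 weeks later |
| First irPD can be overturned | no | yes |
| irRECIST best-response window | closes at first irPD | stays open |

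Footnote 6 leaves some room in the left-hand column: if the first irPD is judged not unequivocal, 8-weekly scans continue. That depends on a judgement which 4.3.1 and 6.4 do not call for.

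**3. Exposure.** Inputs: a cycle of 2 weeks (section 3.1.1), a minimum confirmation interval of 4 weeks (Appendix B 2.4.1), and a scan interval of 8 weeks ±7 days (section 7.2). Extra cycles = interval ÷ cycle length.

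- At the 4-week minimum: 4 ÷ 2 = 2 cycles.
- At the next scheduled scan: 8 ÷ 2 = 4 cycles. With the window, 7 ÷ 2 = 3.5 to 9 ÷ 2 = 4.5.

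In the combination cohort, daily brivanib would continue over the same 4 to 8 weeks. These counts assume that no dose is withheld meanwhile.

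**4. Endpoints.**

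- PFS and TTP by irRECIST: the synopsis does not say whether first or confirmed irPD is the event, or what becomes of an irPD with no later scan.
- ORR by irRECIST: best response is counted only to the end of treatment, so a response after a first irPD can count for the subject kept on drug but not for the one stopped.
- Duration of response: the date rule is already given in Appendix B 2.5.2.
- ORR by RECIST 1.1, assessed by BICR: the irRECIST rule does not enter its definition.

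**The case against.** **The sections can be read together.** Sections 3.1.4 and 4.3.1 refer to irRECIST, the protocol's irRECIST text is Appendix B, and Appendix B contains the confirmation step. On that reading 7.2 only spells out what the other two import, and a stop for progression comes after the confirming scan. This is possible, but no passage says it, and the irPD definitions are met at a single time point.

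**Imaging may continue anyway.** Footnote 6 allows this after equivocal progression, so it would be too strong to say that a confirming scan can never occur. Sections 4.3.1 and 6.4 still point the other way.

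**Details are deferred.** Section 9.3.2 refers to a SAP. No separate SAP text is available here, so a derivation rule may exist elsewhere. It would not settle the stopping and imaging conflict.

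**A stronger reading is tempting.** The word confirmed in the PFS censoring sentence might suggest that an unconfirmed irPD is censored, which would inflate the irRECIST medians. For scale, take the 4.2-month median TTP reported in section 1.1.4.2.2 for single-agent brivanib 800 mg QD and assume exponential times. If a share f of progressions were censored, the TTP median would be 4.2 ÷ (1 − f): 5.6 months at f = 0.25 and 8.4 months at f = 0.50. With 8-weekly scans and censoring at the last progression-free scan, a simulation gives 24, 32 and 40 weeks at f = 0.10, 0.30 and 0.50, against 24 weeks when events are dated at first irPD.

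The documents do not support these as expected effects. The sentence censors only subjects with no documented radiographic progression or death, and a first irPD is naturally documented progression. The shares are assumed, and 4.2 months is not an MGD013 figure. Later deaths remain PFS events, so the formula would apply to TTP at most.

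**Event dating.** A reader might also infer that events move to the confirming scan, a shift of 28 ÷ 30.4 = 0.9 to 56 ÷ 30.4 = 1.8 months. No passage dates progression there, and Appendix B 2.5.2 uses the first date for duration of response.

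**Conclusion.** The conflict is real and should be resolved. Two sections end study drug at irRECIST progression without mentioning confirmation, a third continues drug to confirmation, and the imaging rules do not clearly provide the scan that confirmation needs. For identical scans the difference is about two to four MGD013 cycles, assuming confirmation at the 4-week minimum or at the next 8-week scan with dosing uninterrupted.

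The irRECIST versions of PFS, TTP and ORR depend on which section a site follows. The size of that effect cannot be estimated from the documents, because the share of subjects stopped at first irPD is unknown. A reader might infer that the irRECIST medians are materially overstated, that the effect differs between monotherapy and combination because confirmation depends on tolerability, or that the main result is at risk. The first needs a censoring reading that is possible but not natural. The second has no supporting data here. The third does not follow, since the primary endpoint is BICR-assessed ORR by RECIST 1.1 and the first-stage decisions use investigator-assessed RECIST 1.1 response.

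**What to change.** 1. Reconcile sections 3.1.4, 4.3.1, 6.4 and 7.2, Table 1 footnote 6 and Appendix B 2.4.1, so that one consistent rule governs when treatment stops and when imaging stops. Whether first or confirmed irPD ends treatment is for the sponsor to decide.
2. If confirmation is kept, add irPD to the confirmation sentence in footnote 6 and exempt the confirming scan from the imaging stop in 4.3.1 and 6.4. If first irPD is kept, bring 7.2 into line and say what role the scan in Appendix B 2.4.1 then has.
3. Under either choice, state one event rule for irRECIST PFS and TTP. The event date is the first irPD scan, in line with Appendix B 2.5.2. It counts as an event if confirmed or if no later evaluable scan exists, and it is cancelled only by a later scan that does not show irPD.

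The cost is amendment wording and one derivation rule. Appendix B already requires the confirmatory scan in subjects tolerating treatment, so for them no procedure is added. irRECIST PFS and TTP medians may come out slightly shorter than under a censoring reading.
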